2.7 Safety analyses

The following applies to each of the three cohorts (i.e., symptomatic dermographism, cold urticaria, and cholinergic urticaria) separately, and in the overall CINDU population.

For all safety analyses (i.e. AEs, laboratory data, vital signs, and ECG), the SAF will be used. All data will be included in the analysis regardless of rescue medication use.

All listings and tables will be presented by treatment group.

Treatment groups for evaluation of treatment period

The summaries for evaluation of the treatment periods will allow for comparisons of treatment groups with placebo, before treatment switch is initiated. Therefore, the safety data for the Placebo-Ligelizumab 72mg/120mg q4w group will be provided in two separate periods.

As adverse event tables will be provided for the treatment period up to Week 12 separately, the Week 12 treatment period definition is the treatment period up to Week 12 dosing date (excluding the Week 12 dosing date). For the Placebo-Ligelizumab 72mg/120mg q4w group, if the first dosing date transitioning to ligelizumab happened earlier or later than the Week 12 dosing date (e.g. Week 4 or Week 8) due to a dosing error, the placebo treatment period will be cut-off by all the information prior to the first ligelizumab dosing date. The detailed description of the Week 12 cutoff date definition is provided in the statistical analysis plan appendix.

Treatment groups for evaluation of entire study

The summaries for evaluation of entire study will include all the information following the study design treatment groups. In addition, the following combined groups may be used for safety analysis.

Table 2-3 Treatment groups for safety analysis

	Ligelizumab 72mg q4w	Ligelizumab 120mg q4w	Placebo	Transitioned to Ligelizumab 72mg/120mg q4w
Treatment Period up to Week 12 visit	Yes ^a	Yes ^a	Yes ¹	No
Entire Study	Yes	Yes	No	Yes ²

¹ The information before the treatment switching is initiated will be included. It means only the safety information from the period when participants receive placebo will be included in the analysis.

² The information after the treatment transitioned is initiated will be included. It means only the safety information from the period when participants receive ligelizumab 72mg/120mg q4w will be included in the analysis.

^a The treatment groups will be included in the summary tables include information up to Week 12 visit.

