2.7.1 Adverse events (AEs)

Treatment emergent adverse events (TEAEs) are events which started on or after the first dose of study treatment and within 16 weeks after the last study treatment, or events present prior to the first dose of study treatment but increased in severity based on preferred term within 16 weeks after the last study treatment.

TEAEs will be summarized in each cohort separately by the actually received treatment group:

- The number and exposure-adjusted incidence of subjects having any TEAE by system organ class (SOC) and preferred term (PT): For the participants in the placebo arm, adverse events after switching to ligelizumab (on or after Week 12) will be summarized separately for the treatment phase. The summary of the TEAEs up to Week 12 will include all the TEAEs up to Week 12 for all the treatment groups, including the placebo only group. The summary of the TEAEs for the entire study will be provided for all the treatment groups listed in Table 2-3.
- The number and exposure-adjusted incidence of subjects having any TEAE by severity: if a subject reported more than one adverse event with the same preferred term, the adverse event with the greatest severity will be presented. If a subject reported more than one adverse event within the same primary system organ class, the subject will be counted only once with the greatest severity at the system organ class level, where applicable.
- The number and exposure-adjusted incidence of subjects having any related TEAEs.: if a subject reported more than one adverse event with the same preferred term, the adverse event with the greatest severity will be presented. If a subject reported more than one adverse event within the same primary system organ class, the subject will be counted only once with the greatest severity at the system organ class level, where applicable.
- The number exposure-adjusted incidence of subjects having any serious treatment emergent adverse events (TESAEs), related TESAEs. The following significant adverse event will be listed - TEAEs leading to discontinuation and dose interruption, and TEAE adverse events of special interest (AESIs). For AESIs with adjudication (anaphylaxis, malignancy, CCV), separate listings will be provided based on the adjudicated results.
- A listing will be provided for safety topics of immunogenicity, COVID-19 infection, Liver Toxicity.

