2.7.2 Deaths

Death will be reported as part of TESAE with a fatal outcome and will be listed in separate listings.

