5.2 Derivation rules for Week 12 treatment period

Week 12 treatment period cut-off date

The cutoff date for Week 12 treatment period is defined as below.

For the Placebo-Ligelizumab 72mg/120mg q4w group,

1. The first ligelizumab dosing date will be used if available;
2. Otherwise, if no ligelizumab dosing happened, then the cutoff date = min(end of study date, withdrawal of ICF date, date of death, IA cutoff date(if applicable)).

For other groups,

1. If participants complete treatment period or are still ongoing, the cutoff date is the first non-missing date of the following dates: Week 12 dosing date, Week 12 visit date, PD date of missing visit at Week 12, first dosing date + 12 weeks.
2. If participants early discontinue treatment,
 - a. If last dosing visit is less than Week 12, then the cutoff date = min(end of study date, withdrawal of ICF date, date of death, IA cutoff date(if applicable)).
 - b. If last dosing visit is great than or equal to Week 12, then the cutoff date is the first non-missing date of the following dates: Week 12 dosing date, Week 12 visit date, PD date of missing visit at Week 12, first dosing date + 12 weeks.

Adverse events summary tables:

The summary table is will be generated based on the cut-off date following the definition of “treatment period up to Week 12” in Table 2-5:

Adverse events happened at the same day with this cut-off date NOT included in “treatment period up to Week 12” tables.

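### SAP 5.2 leaves out of the up-to-Week-12 adverse event tables any event starting on the day a participant dies or leaves the study before Week 12

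*SAP*

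**What the plan says.** SAP 2.7 describes the window for the placebo-controlled adverse event tables: "the Week 12 treatment period definition is the treatment period up to Week 12 dosing date (excluding the Week 12 dosing date". It refers to the appendix for the detailed definition.

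The appendix, SAP 5.2, sets the cut-off by branch:

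- **Placebo group, rule 1:** the first ligelizumab dosing date.
- **Placebo group, rule 2:** "if no ligelizumab dosing happened, then the cutoff date = min(end of study date, withdrawal of ICF date, date of death", or an interim cut-off if there is one.
- **Ligelizumab groups, rules 1 and 2b:** the Week 12 dosing date or, failing that, in order: the Week 12 visit date, the protocol-deviation date of the missed visit, first dose plus 12 weeks.
- **Ligelizumab groups, rule 2a (early stoppers):** "last dosing visit is less than Week 12, then the cutoff date = min(end of study date, withdrawal of ICF date, date of death", again with any interim cut-off.

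After all branches comes one general statement: "Adverse events happened at the same day with this cut-off date NOT included in" the up-to-Week-12 tables.

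Treatment-emergent events are defined in SAP 2.7.1 as "events which started on or after the first dose of study treatment and within 16 weeks after the last study treatment", plus pre-existing events that worsen.

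**The concern.** Excluding the cut-off day makes sense when that day is a dosing or switch date, because an event on it may follow the new dose and belong to the next period. A date of death, withdrawal or end of study starts no new period, so an event on that day can belong only to the period that is ending.

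The up-to-Week-12 tables are where SAP 2.7 places the comparison of each group with placebo before the switch. Hypersensitivity including anaphylaxis is an event of special interest, anaphylaxis is adjudicated (SAP 2.7.1.2), and the protocol requires two hours of observation after every dose (Protocol 6.3.2). A reaction that starts and is fatal on a dosing day is the kind of event these tables should show, and the wording drops it.

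**Working it through.** The plan gives no figure on this point. The check applies the rules of SAP 5.2 to test cases.

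**Step 1: which branch applies.** A participant who dies before the Week 12 dose has neither completed treatment nor is ongoing. Rule 2a therefore applies in a ligelizumab arm and rule 2 in the placebo arm. The cut-off is the date of death, unless end of study or withdrawal is dated earlier.

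**Step 2: the inclusion test.** As written, an event is tabulated only if its date is before the cut-off. Study day = event date − first dose date + 1 (SAP 2.1.1.2), so Week 4 is Day 29 and Week 12 is Day 85. I read the event date as the start date. The last column uses the rule proposed under the fix.

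| Case | Rule | Cut-off | AE start | As written | With fix |
|---|---|---|---|---|---|
| Ligelizumab, AE and death on Day 1 | 2a | Day 1 | Day 1 | out | in |
| Ligelizumab, AE and death on Day 29 | 2a | Day 29 | Day 29 | out | in |
| Placebo, never switched, AE and death on Day 29 | Placebo 2 | Day 29 | Day 29 | out | in |
| Ligelizumab, AE Day 29, death Day 31 | 2a | Day 31 | Day 29 | in | in |
| Ligelizumab, AE on Week 12 dosing day | 2b | Day 85 | Day 85 | out | out |
| Placebo, AE on switch day | Placebo 1 | Day 85 | Day 85 | out | out |

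The first three events are treatment-emergent under SAP 2.7.1, so only the cut-off rule removes them. The last two exclusions are the intended ones.

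**Step 3: who can lose an event that belongs in the window.** Treatment stoppers are expected at an end-of-treatment visit 4 weeks after the last dose and then through follow-up (Protocol 9.1.1), which lasts 12 weeks (Protocol 3.1). For those who complete it, end of study is about last dose + 4 + 12 = last dose + 16 weeks:

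- last dose Week 0: Week 16
- last dose Week 4: Week 20
- last dose Week 8: Week 24

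All of these fall after Week 12, so an event on that day is outside the placebo-controlled period anyway. Only death or full study exit before Week 12, with onset on that exact day, loses an event that belongs in the tables.

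**Step 4: illustrative size.** SAP 2.7.1.1 uses events ÷ person-time with an exact Poisson interval. I assume the planned arm sizes and 84 days for every participant (the SAP would stop the clock at the event, a small difference). For 56 per arm, person-time = 56 × 84 / 365.25 = 12.88 years, and one event gives 1 / 12.88 = 7.8 per 100 person-years.

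| Planned arm | Person-years | One event shown: rate per 100 (95% CI) | Event omitted: rate per 100 (95% CI) |
|---|---|---|---|
| 34 | 7.82 | 12.8 (0.3 to 71.3) | 0 (0 to 47.2) |
| 56 | 12.88 | 7.8 (0.2 to 43.3) | 0 (0 to 28.6) |
| 79 | 18.17 | 5.5 (0.1 to 30.7) | 0 (0 to 20.3) |

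**Step 5: where else the event would appear.** On deaths, SAP 2.7.2 says: "Death will be reported as part of TESAE with a fatal outcome and will be listed in separate listings". SAP 2.7.1 also counts deaths from treatment-emergent serious events by system organ class and preferred term, and plans listings of adjudicated events; SAP 2.7.1.2 adds a summary table of them. Ligelizumab-arm events stay in the entire-study tables.

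For a placebo participant who never switched, the position is unclear. SAP 2.7.1 bases the entire-study summary on the Table 2-3 groups. Table 2-3 has No for placebo over the entire study, and its footnote on the transitioned group says that "only the safety information from the period when participants receive ligelizumab 72mg/120mg q4w will be included in the analysis". Table 2-2, however, lists the placebo-to-ligelizumab groups for entire-study safety data. Under Table 2-3 the event would be in neither set of summaries; under Table 2-2 it would be in one.

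**The case against.** The strongest reply is that little is hidden. A death is listed separately, fatal serious events are counted, adjudicated anaphylaxis has its own outputs, and a ligelizumab-arm event remains in the entire-study tables. After termination, SAP 4 rules out statistical analysis and limits output to listings and summary tables, so no formal safety test depends on the rule. The wording is also loose: the date meant is not stated to be the start date, the rule points to a Table 2-5 that cannot be checked in the public text, and SAP 2.7 names only the Week 12 dosing date.

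Most of this stands, and it limits the consequence to one set of tables. It does not remove the defect. SAP 2.7 defers to the appendix, whose general statement carries no exception, and SAP 2.7.1 still plans up-to-Week-12 summaries.

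A reader might infer a much wider loss: about 10% of participants, from the drop-out allowance in Protocol 5, or nearly everyone dosed, because only 3 participants completed Week 12 (SAP 1.1.2) out of 39 enrolled (SAP 1.1). The documents do not support either. The 10% is a study drop-out allowance for sample size, not a rate of exit before Week 12. The 36 of 39 (92%) is an upper bound on how many could fall under rule 2a or placebo rule 2: no dosed count is given, and the SAP's Enrolled set needs only consent and a screening visit. Falling under a rule is also not losing an event, because terminated participants moved into follow-up (SAP 1.1.2) and step 3 applies to those who complete it.

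**Conclusion.** The point holds in a narrow form. Following SAP 5.2 as written omits from the up-to-Week-12 tables an adverse event that starts on the day of death, consent withdrawal or end of study, when that day falls before Week 12 and the participant is under rule 2a or placebo rule 2. The reason implied by SAP 2.7 does not extend to those dates.

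The number of affected events is probably very small and may be zero: the documents report no such case. If one occurred, a planned arm of 56 would show 0 instead of 7.8 per 100 person-years, under the assumptions in step 4. A reader should not conclude that a fatal reaction would vanish from reporting, since the outputs in step 5 still carry it. The weakest cover is for never-switched placebo participants, where Tables 2-2 and 2-3 disagree. The conclusion assumes that the event date is the start date and that the general statement covers every branch, which is its plain reading.

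**What to change.** In SAP 5.2:

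1. Apply the same-day exclusion only when the cut-off is the first ligelizumab dosing date, the Week 12 dosing date, or one of the listed substitutes for the latter (Week 12 visit date, protocol-deviation date of the missed visit, first dose plus 12 weeks).
2. When the cut-off is death, consent withdrawal or end of study and falls before first dose plus 12 weeks, include events with a start date on or before the cut-off. The 12-week limit keeps this change from adding later events to a Week 12 table.
3. Say start date where the text now says that events happened.

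The interim cut-off needs no rule, because the SAP states that no interim analysis will be performed. Separately, reconcile Tables 2-2 and 2-3 for never-switched placebo participants in the entire-study summaries, and confirm the reference to Table 2-5.

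The cost is one sentence and one programming condition. If the tables already exist, a check for events starting on a death or exit date before Week 12 shows whether any output changes.

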## **Adverse events**

All information obtained on AEs will be displayed by treatment group (or sequence) and participant.

Treatment emergent AEs will be summarized by actually received treatment.

Treatment emergent AEs (TEAE) are defined as:

- Events started after the first dose of study treatment (ligelizumab) in this study and within 16 weeks of last dose of study treatment
- Events present prior to the first dose of study treatment (ligelizumab) in this study but:
  1. increased in severity based on preferred term (e.g. worsening of headache),
  2. same PT but increased severity (e.g. from mild to moderate),
  3. same PT but increase in seriousness (from non-serious AE to SAE; if already a SAE from medical significant to LT/fatal)and within 16 weeks after the last dose of the study treatment.

The number (and percentage) of participants with treatment emergent AEs will be summarized in the following ways:

- by treatment, primary system organ class and preferred term.
- by treatment, primary system organ class, preferred term and maximum severity.
- by treatment, Standardized MedDRA Query (SMQ) and preferred term.

Separate summaries will be provided for study medication related AEs, death, SAEs, other significant adverse events leading to treatment discontinuation.

The number (and proportion) of participants with treatment emergent AEs of special interest (AESI) will be summarized by treatment.

The number (and proportion) of participants with treatment emergent AEs related to other safety topics such as events related to “liver toxicity” will be summarized by treatment.

A participant with multiple AEs within a primary system organ class is only counted once towards the total of the primary system organ class.

For the placebo-ligelizumab treatment group, treatment-emergent AEs will be counted separately for the placebo treatment and ligelizumab treatment.

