2.7.1.1 Exposure-Adjusted Incidence Rate

Due to expected differences in exposure and follow-up due to varied duration of study participation between participants, adverse event incidence rates will be provided as “exposure adjusted AE incidence rates”.

The EAIR is defined as the number of subjects with a specific event divided by the total exposure-time among the subjects in the study group. That is, the EAIR is calculated as:

$EAIR = n / \sum t_i$, where n is the number of subjects having the i^{th} type event, and t_i is a subject's exposure time and defined as the shortest of the following:

- 1) time to the first episode of the i^{th} type event (if the event occurs),
- 2) duration of study treatment plus the 16-week washout period (approximately corresponding to five half-lives) after last treatment dose, or
- 3) end of the analysis period (Week 12 for the placebo period, week 36 for all safety follow-up).

The total exposure time of all subjects in a treatment group is $\sum t_i$. The EAIR is interpreted as the number of events occurring in a population per unit time. The exact Poisson 95% confidence interval for the EAIR will be provided as well, where an exact $100*(1-\alpha)\%$ confidence interval will be derived as follows (Garwood 1936, Sahai and Khurshid 1993):

- Lower confidence limit $L = \frac{0.5C_{\alpha/2,2n}}{\sum t_i}$ for $n>0$, 0 otherwise,
- Upper confidence limit $U = \frac{0.5C_{1-\alpha/2,2n+2}}{\sum t_i}$,

where $C_{\alpha,k}$ is the α th quantile of the Chi-square distribution with k degrees of freedom.

Whenever applicable, exposure adjusted incidence rates will be provided for the type as below:

1. TEAE and TESAE: Primary SOC level, PT level
2. Most frequent (at least 5% in any treatment group) TEAE: Primary SOC level, PT level

Treatment emergent AE of special interest.

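### A placebo participant's reaction to the Week 12 provocation test comes before the first ligelizumab dose, but the SAP's day-level rule takes it off placebo and counts it on ligelizumab

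*SAP*

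**What the plan says.** **Order within the visit.** Protocol 3.2 and 8.3.1 forbid dosing before the provocation test. Protocol 4.5 has sites manage a reaction first and dose after recovery. Placebo participants receive placebo at Weeks 0, 4 and 8 and their first ligelizumab dose at Week 12 (Protocol 3.1).

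**Recording.** Protocol 10.1.1 foresees test reactions as adverse events, rates them as not suspected, and asks for start and end dates. It names no start time.

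**Week 12 cut-off.** For the Placebo-Ligelizumab group SAP 5.2 states: "The first ligelizumab dosing date will be used if available". It then says: "Adverse events happened at the same day with this cut-off date NOT included in" the up-to-Week-12 tables. SAP 2.7 likewise ends the Week 12 period before the Week 12 dosing date.

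**After the cut-off.** SAP 2.7.1 says of the placebo arm: "adverse events after switching to ligelizumab (on or after Week 12) will be summarized separately".

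**Table 2-3 (SAP 2.7).** Footnote 1, on the placebo column: "The information before the treatment switching is initiated will be included". Footnote 2, on the transitioned column: "only the safety information from the period when participants receive ligelizumab 72mg/120mg q4w will be included in the analysis". The entire-study row has no placebo column.

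**Treatment-emergent definition.** The SAP counts "events which started on or after the first dose of study treatment"; Protocol 12.5.2 has "Events started after the first dose of study treatment (ligelizumab) in this study".

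**The concern.** The order of test and dose is known in advance at every Week 12 visit. A placebo participant who reacts to the test has had only placebo when the reaction starts. A rule that works by calendar day cannot see this and attributes the event to the drug given afterwards.

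The type of event makes this matter. The test is meant to provoke hives. Urticaria is also among the symptoms that participants are told to watch for after dosing (Protocol 4.5), and hypersensitivity is an adverse event of special interest (SAP 2.7.1.2). A provoked reaction placed in the ligelizumab column can look like a first-dose reaction.

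The exposure-adjusted rate adds a second effect. A participant with the event contributes only the "time to the first episode of the" event type in question (SAP 2.7.1.1). A misplaced same-day reaction therefore ends that participant's ligelizumab clock almost at once and hides any later event of the same type. Efficacy tables were cancelled after termination, but the treatment-emergent tables and their rates are still planned.

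**Working it through.** The plan states no figure on this point, so the check traces the rules and then sizes one event.

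**Trace: placebo participant, Week 12 visit on date D**
1. Test and reaction on D, then the first ligelizumab dose later on D (Protocol 3.2, 4.5).
2. Cut-off date = first ligelizumab dosing date = D (SAP 5.2).
3. Event start date = D = cut-off date, so the event is excluded from the up-to-Week-12 placebo column (SAP 5.2, 2.7).
4. The event falls on Week 12, so it goes to the post-switch summary (SAP 2.7.1). The only column available for the entire study is the transitioned one (Table 2-3).
5. Footnote 1 would put the event on placebo, and footnote 2 would keep it off ligelizumab. The derivation does the opposite of both.

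An onset time on the form would not change this, because the cut-off works by day.

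**Other visits.** At Weeks 4 and 8 the drug before and after the test is the same. In the ligelizumab arms at Week 12, the event leaves the up-to-Week-12 table but stays on the same drug. Only placebo participants at Week 12 are assigned to the wrong drug.

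**The SAP treats that day differently elsewhere.** The concomitant and rescue medication listings keep the transition day with placebo (SAP 2.4.2). The safety baseline uses the dosing time to find the last pre-dose value (SAP 2.1.1.5).

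**Participants exposed**
- Planned placebo participants: 56 + 34 + 79 = 169 (Protocol 3.1).
- At termination: 3 participants, all arms together, had completed Week 12 (SAP 1.1.2). How many were on placebo is not stated, so 0 to 3.
- The share r of placebo participants with a Week 12 test reaction recorded as an adverse event is not in the documents. As an assumption, at the planned size: r = 2%, 5%, 10%, 20% gives 169 × r = 3.4, 8.5, 16.9, 33.8 participants moved.

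**Effect of one event on the rate** (rate = n / Σt; assumed: no other events, follow-up from Week 12 to Week 36 = 24 × 7 = 168 days, and 1 day for the participant who reacts)
- Symptomatic dermographism, combined transitioned column (Table 2-3), 56 participants: 55 × 168 + 1 = 9,241 days; 9,241 / 365.25 = 25.30 patient-years; 1 / 25.30 = 4.0 per 100 patient-years.
- Shown by dose (Table 2-2 labels), 56 / 2 = 28 participants: 27 × 168 + 1 = 4,537 days; 4,537 / 365.25 = 12.42 patient-years; 1 / 12.42 = 8.1 per 100 patient-years.
- Correct value in the ligelizumab column in both cases: 0.

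**The case against.** **Exclusion is not reassignment.** SAP 5.2 only leaves the event out of one table. The main clause of SAP 2.7.1 is about events after switching, with Week 12 in parentheses, and footnote 2 could be read as keeping a pre-dose event out of the transitioned column. But the exclusion from placebo is explicit. If footnote 2 prevailed over the parenthesis, the event would be in no summary column at all, which still breaches footnote 1.

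**Same-day counting on active drug is conservative.** It keeps true post-dose reactions, including those in the two-hour observation period. That is a sound convention when the order is unknown. Here the order is fixed for one identifiable class of events, and only that class needs to move.

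**Expected test responses are efficacy data.** A positive Week 0 test is an entry requirement, and test results have their own place on the eCRF. Protocol 10.1.1 gives causality guidance for reactions that are reported; it does not make every positive test an adverse event. This stands: the number recorded may be small or nil.

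**Safeguards.** Such reactions are rated not suspected, so they should stay out of the related-event table. Anaphylaxis is adjudicated blind, and events of special interest are listed individually. This also stands and lowers the priority.

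Three stronger readings are tempting, and the documents do not support them:
- *Week 0 reactions are counted as treatment-emergent.* The SAP refers to the first dose, not the dosing date, so a pre-dose reaction is excluded on its literal wording. It would be counted only if the rule were applied by date. SAP 5.3.2 covers partial dates and does not settle the matter.
- *The comparison with placebo up to Week 12 is biased.* Events on the Week 12 dosing day are dropped from every arm, and Week 0 tests precede randomization (Protocol 6.4.2).
- *All 39 enrolled participants are affected.* The Protocol glossary places enrollment at consent, and the SAP's Enrolled set needs only consent and a screening visit. The 39 may include people never tested or dosed.

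**Conclusion.** The Week 12 point holds on the text. A placebo participant's pre-dose test reaction, if recorded as an adverse event, is removed from placebo and counted on ligelizumab, against footnotes 1 and 2 of Table 2-3. What is wrong is the content of the transitioned-to-ligelizumab column, not the controlled comparison.

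The exposure was up to 169 planned placebo participants and is 0 to 3 after termination. The 4.0 and 8.1 per 100 patient-years are illustrations of one event in a full-size symptomatic dermographism cohort followed to Week 36, not estimates. The Week 0 wording is a matter for clarification only. The priority is minor.

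**What to change.** In SAP 2.7.1 and 5.2:
- Assign an adverse event recorded as a reaction to a provocation test done before the first ligelizumab dose to the placebo period. Keep all other events of that day on ligelizumab.
- If these events then enter the up-to-Week-12 table, apply the same pre-dose rule to Week 12 test reactions in the ligelizumab arms. Otherwise the correction would itself unbalance a comparison that is now even.
- Query adverse events dated on the switch day where the order relative to the dose is not recorded.
- State that a Week 0 reaction starting before the first dose is not treatment-emergent unless it worsens after the dose.

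The cost is one derivation rule, one clarifying sentence, and Week 12 queries on at most 3 visit-days. Design, dosing, stopping criteria and sample size do not change.
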